#### **9.6.1.2. Secondary Efficacy Endpoints - (Weeks 0 - 16)**

Descriptive statistics will be presented for all secondary endpoints in [Table 2](#). Specifically, for continuous endpoints, descriptive statistics (n, mean, standard deviation, median, minimum, and maximum) for baseline, Week 16 and Week 16 change from baseline will be provided. Binary endpoints will be summarized with frequency tabulations.

Treatment comparisons between the apremilast 30 mg BID and placebo will be performed for the secondary endpoints. Continuous efficacy endpoint will be analyzed using the analysis of covariance (ANCOVA) model adjusted for PPPASI total score range ( $\leq 20$  score, 21-30 score,  $\geq 31$  score) and focal infection status (yes, no) at baseline as factors, and the associated baseline value as covariate, while binary endpoints will be evaluated using the CMH test previously described for the primary endpoint. The primary missing data handling approach for continuous endpoint will be multiple imputation (MI).

Secondary efficacy endpoints will be tested without multiplicity adjustment, therefore the p-value for those endpoints will be regarded as nominal. For secondary efficacy endpoints, the two-sided 95% CI will be provided.

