4.2.2. Secondary Efficacy Endpoint(s)

The secondary endpoints include below.

Table 2: Secondary Efficacy Endpoints

Assessment	Description	Timeframe
PPPASI: PPPASI-50	Achieving a PPPASI-50 response	By visit in double blind, placebo-controlled phase
PPPASI: PPPASI-75	Achieving a PPPASI-75 response	By visit in double blind, placebo-controlled phase
PPPASI total score	AUC	Week 0-16
	Percent change from baseline.	By visit in double blind, placebo-controlled phase
PPSI total score	AUC	Week 0-16
	Percent change from baseline	By visit in double blind, placebo-controlled phase
PGA score for palms and soles	Change from baseline	By visit in double blind, placebo-controlled phase
	Achieving a PGA score of cleared (0) or minimal (1)	By visit in double blind, placebo-controlled phase
	Achieving a PGA score of cleared (0) or minimal (1) with at least a 2-grade improvement	By visit in double blind, placebo-controlled phase
SRO: Subject's VAS assessment for PPP symptoms	Change from baseline	By visit in double blind, placebo-controlled phase (except for baseline)
AUC = Area under the curve; PGA = Physician's Global Assessment; PPP = Palmoplantar Pustulosis; PPPASI = Palmoplantar Pustular Psoriasis Area Severity Index; PPPASI-50 = defined as $\geq 50\%$ improvement in PPPASI total score from baseline; PPPASI-75 = defined as $\geq 75\%$ improvement in PPPASI total score from baseline; PPSI = Palmoplantar Severity Index; SRO: Subject's Reported Outcome; VAS = Visual Analogue Scale.		

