10.3.2. Continuous Variables

The continuous variables for secondary and exploratory endpoints in placebo-controlled phase include the following:

- AUC for PPPASI total score from baseline through Week 16
- PPPASI total score change from baseline at Week 16
- AUC for PPSI total score from baseline through Week 16
- PPSI total score change from baseline at Week 16
- AUC for modified PPPASI total score from baseline through Week 16
- Modified PPPASI total score change from baseline at Week 16
- Subject's assessment for PPP sign/finding (PPSI total score) at Week 16

The analysis of covariance (ANCOVA) model with treatment and stratification factor as the fixed effects, the associated baseline value as the covariate and multiple imputation (MI) method to impute the missing data will be applied. Within-group least-squares (LS) means, the associated standard error (SE), and treatment differences in LS means, the associated SE, and associated 2-sided 95% CIs and 2-sided p-values (nominal) will be derived from the model.

Missing value of at Week 16 will be imputed using the MI method ([SAS Institute Inc. 2015](#)) except for AUC. The SAS procedure MI will be used to impute missing scores to create M=100 complete data sets. The missing data patterns will be checked by treatment at baseline, and Week 2, 4, 6, 8, 10, 12, 14, and 16. If there are non-monotone missing patterns, following two separate imputation procedures will be used to complete the imputation process.

1. In the first step, the Markov Chain Monte Carlo (MCMC) method will be used to impute missing scores by treatment to create M=100 imputed data sets with monotone missing patterns. The minimum and maximum values for imputation will correspond to the lowest and the highest scores. The seed will be set at random, a single chain will be used to produce imputations. In case there are convergence issues, a simple model will be used to impute the

CC-10004 (Apremilast)

Statistical Analysis Plan. Protocol CC-10004-PPP-001

missing scores by treatment, with further simplification by dropping both treatment and stratification factor in imputation model if necessary.

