2. In the second step, the predictive mean matching method will be used to impute the remaining missing values for the 100 data sets with monotone missing patterns. The MONOTONE REGPMM statement will be used with a random seed. The missing values at each visit will be imputed based on treatment and previous visits. The number of closest observations to be used in the selection will be K=2.

After the completion of imputation, the same analysis method/model will be used to analyze the 100 complete data sets and the SAS procedure MIANALYZE will be used to combine the results for the statistical inferences.

Following continuous variables for secondary and exploratory endpoints will be summarized by time point. Change and percent change from baseline will be provided. The mixed-effect model for repeated measures (MMRM) will be applied for the endpoints; PPPASI and modified PPPASI, PPSI, and subject's VAS assessment for PPP symptoms. The MMRM model will use the change from baseline as the response variable and include treatment group, visit time, treatment-by-time interaction, and stratification factor as fixed effects, and the baseline value as a covariate. An unstructured covariance matrix will be used to model the correlation among repeated measurements. Within-group LS means and the associated SEs and 2-sided 95% CIs, treatment differences in LS means and the associated 2-sided 95% CIs and 2-sided p-values (nominal) will be derived from the MMRM model.

- PPPASI total score
- Individual PPPASI sub-score (Erythema, Pustules/Vesicle, Desquamation/Scale) change and percent change from baseline at each visit
- PPSI total score
- Subject's VAS assessment for PPP symptoms
- Modified PPPASI total score
- Modified PPPASI sub-score (Pustules, Vesicle)
- Subject's assessment for PPP sign/finding (PPSI total score)
- DLQI
- EQ-5D index value
- EQ-5D VAS

Analyses of time to PPPASI response during the placebo-controlled phase will use Kaplan-Meier method to estimate the median response time and its 2-sided 95% CIs. The stratified log-rank test will be used for calculating 2-sided p-values (nominal) for treatment comparison. The hazard ratio and 2-sided 95% CIs will be estimated using a stratified Cox model. For the time to PPPASI response, the baseline score will be included as covariate in the Cox model. The treatment comparison will only be conducted if appropriate. Kaplan-Meier curves for time to event endpoints will be provided.

CC-10004 (Apremilast)

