10.3.3. Categorical Variables

A shift table from baseline to applicable analysis visits will be provided for the categorical variables including PPSI score, PGA score for palms and soles, and subject's assessment for PPP Sign/Finding using PPSI score.

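### PGA change from baseline is a declared secondary endpoint, but the SAP gives it only a by-visit shift table and leaves it out of the ANCOVA, MMRM and by-visit change lists, contrary to Protocol 9.6.1.2 and SAP 15

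*SAP*

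**What the plan says.** **Endpoint.** SAP Table 2 lists "PGA score for palms and soles" with three secondary endpoints: change from baseline, a score of 0 or 1, and a score of 0 or 1 with at least a two-grade improvement. All three are by visit in the placebo-controlled phase. Protocol Table 2 declares the same three.

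**Protocol commitment (9.6.1.2).** "Descriptive statistics will be presented for all secondary endpoints in" its Table 2. It continues: "Treatment comparisons between the apremilast 30 mg BID and placebo will be performed for the secondary endpoints". For the method: "Continuous efficacy endpoint will be analyzed using the analysis of covariance (ANCOVA) model adjusted for PPPASI total score range", with focal infection status and the endpoint's own baseline value also in the model, and multiple imputation (MI) for missing data. For precision: "For secondary efficacy endpoints, the two-sided 95% CI will be provided".

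**SAP analysis.** Section 10.3.2 opens with "The continuous variables for secondary and exploratory endpoints in placebo-controlled phase include the following", followed by seven items for ANCOVA with MI. It then gives a list of variables to be summarised by time point, and says that the MMRM "will be applied for the endpoints; PPPASI and modified PPPASI, PPSI" and the subject's VAS. PGA appears in none of these. Section 10.3.3 states that a "shift table from baseline to applicable analysis visits will be provided for the categorical variables including PPSI score, PGA score for palms and soles", together with the subject's own signs/findings score. Section 15 reports that the protocol's statistical section is unchanged.

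**The concern.** The protocol treats PGA change from baseline as an endpoint in its own right, separate from the responder rates, and commits to comparing the arms on it. The SAP tells the programmer to produce only a cross-tabulation of baseline grade against later grade. A shift table shows movement within each arm. It yields no treatment difference and no interval.

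Two things follow. A team programming from the SAP alone would report a declared secondary endpoint with no estimate of effect. A team that noticed the gap later would have to choose between ANCOVA at Week 16, the MMRM used for the other scores, or an ordinal method, and could be doing so with treatment codes in hand. SAP 15 says there is no departure, so a reader of the SAP is not alerted to any of this.

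**Working it through.** No figure in the plan bears on this point, so the check is a comparison of lists.

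**Step 1. Which analyses does SAP section 10.3 name for each score?**

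| Score | Status in SAP | Week 16 ANCOVA/MI | MMRM | By-visit change summary | Shift table |
|---|---|---|---|---|---|
| PPPASI total | Secondary | Yes | Yes | Yes | Not named |
| PPSI total | Secondary | Yes | Yes | Yes | Yes |
| Subject's VAS | Secondary | Not named | Yes | Yes | Not named |
| **PGA (change)** | **Secondary** | **Not named** | **Not named** | **Not named** | **Yes** |
| Modified PPPASI total | Exploratory | Yes | Yes | Yes | Not named |
| Subject's signs/findings (PPSI scale) | Exploratory | Yes | Not named | Yes | Yes |
| DLQI, EQ-5D | Exploratory | Not named | Not named | Yes | Not named |

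For PGA change the count is 0 of 7 ANCOVA items, 0 of 4 MMRM endpoints and 0 of 10 by-time-point items.

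**Step 2. Is the shift table meant to replace the change analysis?** The pattern argues against it. The PPSI score and the subject's signs/findings score are also called categorical in 10.3.3, yet both keep a change analysis in 10.3.2. PGA is the only score in that section to lose it. PGA is also the only score behind a continuous secondary endpoint that enters no model, and it gets less than the exploratory DLQI and EQ-5D, which at least have change summaries.

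**Step 3. Are the data there?** Protocol Table 5 schedules PGA at baseline and at Weeks 2, 4, 6, 8, 10, 12, 14 and 16, which is 8 post-baseline visits. Nothing further needs collecting.

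**Step 4. Does the gap extend past Week 16?** Yes, descriptively. SAP Table 3 declares PGA change by visit in the active treatment phase as exploratory. Protocol 9.6.1.3 and 9.6.3 call for descriptive changes from baseline for continuous variables in that phase. The by-time-point list that would deliver them omits PGA.

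**Step 5. Does this touch the design?** No. The stated sample size rests only on PPPASI-50 rates of 45% and 20% at two-sided 0.10 and 80% power. With mean rate 0.325, the uncorrected chi-square formula gives n per arm = [1.645 × √(2 × 0.325 × 0.675) + 0.842 × √(0.45 × 0.55 + 0.20 × 0.80)]² / 0.25² = (1.090 + 0.537)² / 0.0625 ≈ 42.3. That rounds up to 43 per arm, or 86 in total, as the plan states (power 80.5% at 43 per arm). PGA plays no part in it.

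**The case against.** The case on the other side has five parts.

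- **PGA is summarised by visit.** This stands. A reader might infer from 10.3.2 that PGA change has no by-visit summary at all. The shift table in 10.3.3 is one, and a natural one for a six-level grade. What it lacks is a comparison between arms.
- **The protocol's ANCOVA still governs.** This largely stands. A reader might infer that any later analysis of PGA change would be post hoc. The documents do not support that: Protocol 9.6.1.2 already fixes the model, the covariates, MI and the interval, and SAP 15 leaves that section in force. What is not settled is whether an MMRM or an ordinal method is also used, and how the by-visit results are presented.
- **The ANCOVA list is open-ended.** It is introduced as including its items, so PGA is not strictly excluded. That holds for that list only. The MMRM sentence names its endpoints, and the by-time-point list is presented as the set to be summarised.
- **PGA is estimated elsewhere.** This stands for the two responder endpoints. SAP 10.3.1 gives them by-visit proportions, CMH-weighted differences, 95% CIs and nominal p-values. They are separate declared endpoints, and estimating them does not discharge the commitment on the change score.
- **Secondary results are nominal, and SAP 10 disclaims inferential testing beyond the primary endpoint.** This limits the consequence but does not remove the gap. SAP 10.1 and Protocol 9.6.1.2 both keep nominal p-values for secondary endpoints, and for PGA change even the descriptive mean is unlisted.

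The ordinal nature of PGA could justify a different method. The SAP would then need to say so in section 15, and it does not.

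**Conclusion.** The point holds as an undeclared conflict between the SAP and the protocol. One declared secondary endpoint, out of ten rows in SAP Table 2, has no SAP-specified mean change, treatment difference, 95% CI or nominal p-value at any of its 8 post-baseline visits to Week 16. As extracted, Protocol Table 2 shows nine secondary rows because VAS falls under exploratory. That may be a break in the table, and nothing here depends on it.

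The finding assumes that the MMRM sentence and the by-time-point list are meant to be complete, as their wording indicates. It does not extend to saying that PGA is unanalysed, that the endpoint has no pre-specified method anywhere, or that the trial's main conclusion is at risk. The primary analysis and sample size are unaffected. It should be corrected because the conflict is plain and the correction is small.

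**What to change.** Before the Week 16 data are unblinded, amend SAP 10.3.2 as follows.

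1. Add PGA score for palms and soles, change from baseline at Week 16, to the ANCOVA/MI list. This applies the protocol's own model. The existing rule that bounds imputed values by the lowest and highest scores then means 0 and 5.
2. Add the same variable to the MMRM endpoints and to the by-time-point list, as for the other by-visit scores, with 95% CI and nominal p-value. State that only change is reported for PGA. That list otherwise calls for percent change as well, which neither document declares for PGA. This entry also closes the descriptive gap in the active treatment phase.
3. Keep the shift table as a supplement.

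If the sponsor prefers categorical-only handling, the alternative is to declare and justify it in SAP 15 as a departure from Protocol 9.6.1.2.

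The cost is a few words in the SAP and one more table, with no new data. The statistical price is treating a 0 to 5 ordinal grade as continuous, which an endpoint defined as change from baseline already implies.

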4.2.4. Derivation of Efficacy Endpoints

The definition and derivation of efficacy endpoints are described below and in the appendices of the protocol. Change from baseline is calculated as post-baseline visit value - the baseline value. Percent change from baseline is defined as $100 \times \text{change from baseline}/\text{baseline value} (\%)$. Baseline definition for all efficacy endpoints is given in [Section 5.3](#). Handling of time points is described in [Section 5.4](#).

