4.3. Stratification, Randomization, and Blinding

At Visit 2 (Week 0 [Day 1]), subjects who meet eligibility criteria will be randomized using a permuted block randomization in parallel with 1:1 ratio to receive either apremilast 30 mg BID or placebo, using a centralized Interactive Response Technology (IRT). Eligible subjects will be stratified according to a subject's rounded PPPASI score (≤ 20 / 21-30 / ≥ 31) at randomization and whether a subject has or not any focal infection (yes/no) at randomization.

This study will be conducted as a double-blind study for the placebo-controlled treatment phase. During the active treatment phase, the IP will remain blinded, to prevent study personnel and subjects from knowing the IP assignment in the placebo-controlled phase. After 16 weeks of treatment, all subjects originally randomized to the placebo arm at the baseline visit will be switched to receive apremilast 30 mg BID.

The primary data analysis will be conducted after all subjects have completed the Week 16 visit (or discontinued from the study). However, unblinded data will only be made available to selected sponsor and contract research organization (CRO) team members involved with analysis of the data. Prior to the primary data analysis, the selected sponsor and CRO team members will be required to give their consent to declare not to disclose any subject-level data to maintain the data integrity of this study. All other sponsor, site, and CRO personnel directly involved with the conduct of the study, will remain blinded to treatment assignments until the final database lock at the end of the study.

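### The MMRM gives baseline a single slope for all visits; if response scales with baseline and grows over time, its Week 16 intervals are modestly too wide, and a baseline-by-visit term corrects this

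*SAP*

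**What the plan says.** SAP 10.3.2 specifies an MMRM for PPPASI, modified PPPASI, PPSI and the symptom VAS. On the outcome: "The MMRM model will use the change from baseline as the response variable". The mean model contains "treatment group, visit time, treatment-by-time interaction, and stratification factor as fixed effects, and the baseline value as a covariate". On the covariance: "An unstructured covariance matrix will be used to model the correlation among repeated measurements". Time is crossed with treatment only, so the baseline slope and the stratum effects are the same at every visit. Neither document mentions a baseline-by-visit term.

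The placebo-controlled phase has eight post-baseline visits, as the imputation text in the same section shows: "The missing data patterns will be checked by treatment at baseline, and Week 2, 4, 6, 8, 10, 12, 14, and 16". The model is used for reported results: "treatment differences in LS means and the associated 2-sided 95% CIs and 2-sided p-values (nominal) will be derived from the MMRM model".

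SAP 10.3.2 also has a separate Week 16 ANCOVA, in which "the associated baseline value as the covariate and multiple imputation (MI) method to impute the missing data will be applied". It covers PPPASI, modified PPPASI, PPSI and the subject's own sign assessment, but not the symptom VAS. Protocol 9.6.1.2 names only this ANCOVA approach for continuous secondary endpoints.

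**The concern.** The trial measures benefit relative to baseline, through PPPASI-50, PPPASI-75 and percent change (SAP 4.2.4: "Percent change from baseline is defined as" change divided by baseline). A subject who improves by a fraction p changes by -p times baseline on the absolute scale that the MMRM uses. If the mean p grows from Week 2 to Week 16, so does the slope of change on baseline.

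A common slope cannot follow that. Residual variance is smaller early on, so the fitted slope sits near the early-visit value, and the missed baseline effect at Week 16 is counted as noise. Because randomization is stratified on baseline severity ("Eligible subjects will be stratified according to a subject's rounded PPPASI score"), the arms are already fairly balanced on baseline. The model's standard error can therefore exceed the actual sampling variability of the estimate. At stake is the width of the MMRM intervals and the size of their nominal p-values, not the direction of any result.

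**Working it through.** **Plan's own figure.** The documents give no standard error for the MMRM. The figure used for calibration is the sample size in SAP 4.4: 45% against 20%, chi-square, two-sided 0.10, 80% power.

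n per arm = [1.645·√(2·0.325·0.675) + 0.842·√(0.45·0.55 + 0.20·0.80)]² / 0.25² = (1.090 + 0.537)² / 0.0625 ≈ 42.4, so 43 per arm and 86 in total. Power at 43 per arm is 80.5%. The plan's figure is reproduced.

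**Week 16 slope implied by those rates.** Assume percent improvement is normal with SD 30 points.
- Apremilast mean: 50 - 0.126·30 ≈ 46%.
- Placebo mean: 50 - 0.842·30 ≈ 25%.
- Pooled: about 36%, so a Week 16 slope near -0.36.

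**Mechanism.** With unstructured covariance S and true visit slopes b, the common slope tends to (1'S⁻¹b)/(1'S⁻¹1). The Week 16 residual variance σ² rises by (b₁₆ - b_common)²·Var(baseline). In the main case the common slope is about -0.06, a gap of 0.295 before rounding. With baseline mean 26 and SD 10, σ = 0.30·26 = 7.8 and σ² = 60.8. Expected ratio of standard errors: √(1 + 0.295²·100/60.8) = 1.07.

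**Simulation.** 86 subjects, stratified permuted blocks, eight visits, REML with unstructured covariance, 400 replicates per scenario. Assumptions not in the documents: baseline mean 26 and SD 6, 10 or 14 (the minimum of 12 is from protocol 4.2); improvement SD 30 or 20 points; correlation 0.85 per two weeks; residual SD growing with time; dropout 0 to 20%; block size 4; focal infection in 50%. The main case is linear growth, baseline SD 10, improvement SD 30 and 10% dropout. Other rows change only what they name.

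| Scenario | Week 16 SE, SAP model | SE with baseline-by-visit | Ratio |
|---|---|---|---|
| Main case | 1.854 | 1.749 | 1.060 |
| Early plateau | 1.802 | 1.749 | 1.030 |
| Baseline SD 6 | 1.793 | 1.751 | 1.024 |
| Baseline SD 14 | 1.919 | 1.758 | 1.092 |
| No dropout | 1.801 | 1.689 | 1.066 |
| Dropout 20% | 1.918 | 1.805 | 1.062 |
| Noise proportional to baseline | 1.942 | 1.831 | 1.061 |
| Same, early plateau | 1.893 | 1.831 | 1.034 |
| Improvement SD 20 | 1.362 | 1.166 | 1.168 |
| Improvement SD 20, baseline SD 14 | 1.465 | 1.172 | 1.250 |
| Effect complete by Week 2 | 1.745 | 1.749 | 0.998 |
| Improvement unrelated to baseline | 1.732 | 1.736 | 0.998 |

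**Calibration.** In the ten scenarios where the slope steepens, the SAP model's standard error exceeds the estimator's own sampling SD by 1.5 to 16%, with coverage of 95.3 to 98.3%. The models with by-visit slopes are within 4% either way. One such ratio carries about 3.5% Monte Carlo error, so the low end cannot be told from zero. The paired ratios in the table are much more precise.

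**Loss of true precision.** This is smaller. With baseline SD 14 the sampling SDs are 1.778 and 1.729 (2.8%); with baseline SD 6 they are 1.700 and 1.696 (0.2%). The point estimate moves by less than 0.1 point.

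**Symptom VAS.** A separate check used six visits, an assumed baseline SD of 27 before truncation to 0-100, Week 16 residual SD 20 to 24, and slopes from -0.15 or -0.20 up to -0.35 or -0.50. The widening was 0.2 to 3.5%.

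**The case against.** Four points can be made against this, and each stands in part.

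- **The premise is not shown.** Protocol 1.3.2 says the time to maximal effect in this population is unknown, and neither document gives a baseline SD, residual SD or slope. This stands: the widening is conditional and vanishes if the slope is constant. But the term then costs nothing measurable (ratio 0.998), so not knowing the time course is no reason to leave it out.
- **Week 16 is already covered.** The ANCOVA fits its own Week 16 slope for PPPASI, modified PPPASI and PPSI. This stands for those scores at Week 16. It does not cover the symptom VAS, which SAP Table 2 lists as secondary, or comparisons before Week 16. For those the MMRM is the only model specified.
- **The consequence is small.** The results are nominal (SAP 10.1) and the error is conservative. In the main case the 95% half-width grows by 1.96·(1.854 - 1.749) ≈ 0.2 points on a 72-point scale. This stands.
- **Larger figures do not fit the design.** A reader might infer a widening of 12 to 15% or 22 to 29%, which simulation gives if the Week 16 slope is -0.45 or -0.60. With improvement SD 20 to 30 points, those slopes imply about 40 to 43% or 63 to 69% responders overall, against a pooled 32.5% in SAP 4.4.

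A reader might also turn a 12 to 15% larger standard error into a loss of 20 to 25% of the sample (1 - 1/1.12² to 1 - 1/1.15²). That treats a miscalibrated standard error as lost information. In those same simulations the sampling SDs are 1.380 against 1.329 and 1.852 against 1.757, ratios of 1.038 and 1.054, or about 7 to 10% of the sample. At a slope of -0.30 the ratio is 1.013, or 2 to 3%.

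**Conclusion.** The point holds as a modest, conditional one. The MMRM in SAP 10.3.2 constrains the baseline slope to be equal at all visits. If improvement is roughly proportional to baseline and grows to Week 16, the reported Week 16 standard error and CI for PPPASI-type scores are about 3 to 9% too wide in most scenarios matching the 45% and 20% response rates. Low residual noise takes this to 17%, and low noise with a wide baseline spread to 25%; wide spread alone gave 9.2%. For the symptom VAS the effect is probably smaller, and PPSI was not simulated. All sizes rest on the assumed baseline and residual spread and on the assumed time course.

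The documents do not support the reading that the intervals are certainly too wide, that the treatment estimate is biased, or that the primary result is weakened. The PPPASI-50 chi-square test and the Week 16 ANCOVA are untouched.

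**What to change.** In SAP 10.3.2, add a baseline-by-visit interaction to the MMRM fixed effects, before the Week 16 unblinding that SAP 2 sets as the deadline for finalizing the plan. This costs one phrase and seven parameters over eight visits (five for the symptom VAS, which has six visits), with no new data. Letting the stratum effects vary by visit as well is optional: in the simulations it changed the Week 16 standard error by less than 1%.
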